8.1. Efficacy Assessments

Efficacy will not be evaluated in this Phase 1 study in healthy volunteers.

8.2. Safety Assessments

Planned timepoints for all safety assessments are provided in the SoA ([Table 1](#)).

8.2.1. Physical Examinations

A complete physical examination will be performed as outlined in the SoA, by the investigator or a licensed health professional listed on Form FDA 1572.

- A complete physical examination will include, at a minimum, assessments of the general appearance of the subject and the HEENT (head, eyes, ears, nose, and throat), cardiac, respiratory, GI, musculoskeletal, neurological, and dermatological systems. Rectal examination should be performed at each physical examination; the rectal examination at all timepoints should include a digital rectal examination and inspection of the perianal area for redness or irritation.
- Height (only at Screening) and weight will also be measured and recorded.
- Investigators should pay special attention to clinical signs related to previous serious illnesses, which will be reason for exclusion from the study.
- Any physical examination abnormality that the investigator considers to be potentially clinically significant and changed from baseline will be reported as an AE.

8.2.2. Vital Signs

Vital signs will be performed as outlined in the SoA ([Table 1](#)).

- Oral temperature, pulse rate, and blood pressure will be assessed.
- Blood pressure and pulse measurements will be assessed with a completely automated device. Manual techniques will be used only if an automated device is not available.
- Blood pressure and pulse at 0.5 hours postdose on Day 1 will be assessed in a side-lying position (consistent with the position required following dosing).
- Blood pressure and pulse at the 2, 4, and 8 hour postdose timepoints should be preceded by at least 5 minutes of rest for the subject in a quiet setting without distractions (eg, television, cell phones).
- At all other timepoints, blood pressure and pulse measurements will be assessed in a supine and standing position (for calculation of orthostatic measurements). For orthostatic blood pressure and pulse measurements, the subject must lie quietly for ≥ 5 minutes before supine/semisupine blood pressure and pulse measurements are taken, then assume a standing position for 3 minutes before standing blood pressure and pulse measurements are taken. If a subject has orthostatic symptoms upon standing (eg, palpitation, dizziness), they will be assisted and asked to lie down without waiting the 3 minutes for vital sign assessment. At the discretion of the investigator, orthostatic measurements may be taken at other vital signs collection timepoints if clinically indicated.
- When applicable, vital signs measurements will be obtained immediately before blood draws.

8.2.3. Electrocardiograms

- Triplicate 12-lead ECG will be obtained as outlined in the SoA ([Table 1](#)) using an ECG machine that automatically calculates the heart rate and measures PR, QRS, QT, and QTcF intervals.
- ECGs should be obtained after the subject has been supine for at least 5 minutes.
- At each time point at which triplicate ECG are required, 3 individual ECG tracings should be obtained as closely as possible in succession, but no more than 2 minutes apart. The full set of triplicates should be completed in less than 4 minutes.

8.2.4. Clinical Safety Laboratory Assessments

- See Appendix 2/Section [10.2](#) for the list of clinical laboratory tests to be performed and the SoA ([Table 1](#)) for the timing and frequency. All protocol-required laboratory assessments must be conducted in accordance with the laboratory manual and the SoA.
- The investigator must review the laboratory report, document this review, and record any clinically relevant changes occurring during the study in the AE section of the

case report form (CRF). The laboratory reports must be filed with the source documents.

- All laboratory tests with values considered clinically significantly abnormal during participation in the study or within 14 days after the dose of study drug should be repeated until the values return to normal or baseline or are no longer considered clinically significant by the investigator or medical monitor.
 - If such values do not return to normal/baseline within a period of time judged reasonable by the investigator, the etiology should be identified and the sponsor notified.
 - If laboratory values from non-protocol-specified laboratory assessments performed at the institution's local laboratory require a change in subject management or are considered clinically significant by the investigator (eg, SAE or AE or dose modification), then the results must be recorded in the eCRF.

8.3. Adverse Events and Serious Adverse Events

The definitions of AEs and SAEs can be found in Appendix 3/Section [10.3](#).

AEs will be reported by the subject (or, when appropriate, by a caregiver, surrogate, or the subject's legally authorized representative).

The investigator and any qualified designees are responsible for detecting, documenting, and recording events that meet the definition of an AE or SAE and remain responsible for following up AEs that are serious, considered related to the study intervention or study procedures, or that caused the subject to discontinue study drug (see Section [7](#)).

8.3.1. Time Period and Frequency for Collecting AE and SAE Information

All AEs and SAEs will be collected from the signing of the ICF until completion of study participation (ie, early termination or Follow-up Phone Call) at the timepoints specified in the SoA ([Table 1](#)).

Any medical condition that is present at the time that a randomized subject is screened and does not deteriorate (worsen in severity and/or frequency) should be recorded as Medical History and not as an AE. However, if the subject's condition deteriorates at any time during the study, it will be recorded as an AE. AEs characterized as intermittent require documentation of onset and duration of each episode. Pretreatment AEs will be collected and captured in the subject's source documentation from the time the subject signs the ICF until the subject receives study drug. Pretreatment AEs in randomized subjects will additionally be entered on the AE page of the subject's eCRF. Laboratory abnormalities, changes in vital signs, and physical examination findings should be considered AEs and reported on the AE page of the subject's eCRF only if the investigator considers them clinically significant and/or they necessitate intervention.

All SAEs will be recorded and reported to the sponsor or designee immediately and under no circumstance should this exceed 24 hours, as indicated in Appendix 3/Section [10.3](#). The investigator will submit any updated SAE data to the sponsor within 24 hours of it being available.

Investigators are not obligated to actively seek AEs or SAEs after the conclusion of study participation. However, if the investigator learns of any SAE, including a death, at any time after a subject has been discharged from the study, and he/she considers the event to be reasonably related to the study intervention or study participation, the investigator must promptly notify the sponsor.

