^a Subjects will be discharged on Day 2 unless they have physical examination findings or laboratory abnormalities that are considered by the investigator to be clinically meaningful. In the event that a subject discontinues from the study, an early termination visit will be performed prior to discharge from the CRU. The early termination assessments will be the same as those conducted at Discharge (Day 2). Every effort should be made and documented to ensure that safety procedures scheduled for Discharge are performed at the early termination visit.

^b Height will only be measured at the Screening Visit. At Check-in (Day -1) and Discharge (Day 2), subjects will be weighed in the morning upon awakening and before they ingest any water or food.

^c Rectal examination should be performed at each physical examination; the rectal examination at all timepoints should include a digital rectal examination and inspection of the perianal area for redness or irritation.

^d Vital signs will include oral temperature, blood pressure, and pulse rate. Side-lying blood pressure and pulse will be obtained at the 0.5 hour postdose timepoint on Day 1 (consistent with the position required following dosing). Blood pressure and pulse at the 2, 4, and 8 hour postdose timepoints should be preceded by at least 5 minutes of rest for the subject in a quiet setting without distractions (eg, television, cell phones). At all other timepoints (ie, predose and 1, 6, and 24 hours postdose), orthostatic blood pressure and pulse measurements will be obtained; subject must lie quietly for ≥5 minutes before supine/semisupine blood pressure and pulse measurements are taken, then assume standing position for 3 minutes before standing blood pressure and pulse measurements are taken. If a subject has orthostatic symptoms upon standing (eg, palpitation, dizziness), they will be assisted and asked to lie down without waiting the 3 minutes for vital sign assessment. Orthostatic measurements may be taken at other vital signs collection timepoints if clinically indicated, at the discretion of the investigator. When applicable, vital sign measurements will be obtained immediately before blood draws.

^e ECGs should be obtained after the subject has been supine for at least 5 minutes. At each timepoint required, 3 individual ECG tracings should be obtained as closely as possible in succession, but no more than 2 minutes apart. The full set of tracings should be completed in less than 4 minutes.

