7. DISCONTINUATION OF STUDY INTERVENTION AND SUBJECT DISCONTINUATION/WITHDRAWAL

7.1. Discontinuation of Study Intervention

It is not anticipated that it will be necessary for a subject to permanently discontinue (definitive discontinuation) study intervention during this single-dose study. In rare instances, a subject may withdraw from the study prior to completion of the Clinic Period; see the SoA ([Table 1](#)) for data to be collected at the time of discontinuation and follow-up and for any further evaluations that need to be completed. If a subject is discontinuing due to an AE, the AE must be followed until it is resolved, stable, or judged by the investigator to be not clinically significant.

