7.2. Subject Discontinuation/Withdrawal from the Study

- A subject may withdraw from the study at any time at his/her own request or may be withdrawn at any time at the discretion of the investigator for safety, behavioral, compliance, or administrative reasons. This is expected to be uncommon.
- At the time of discontinuation from the study, if possible, an early discontinuation visit should be conducted, as shown in the SoA ([Table 1](#)). See SoA for data to be collected at the time of study discontinuation and follow-up and for any further evaluations that need to be completed.
- The subject will be permanently discontinued both from the study intervention and from the study at that time.

- If the subject withdraws consent for disclosure of future information, the sponsor may retain and continue to use any data collected before such a withdrawal of consent.
- If a subject withdraws from the study, he/she may request destruction of any samples taken and not tested, and the investigator must document this in the site study records.

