10.3.1.2. TEAE Definition

- A TEAE is an event that emerges, or a pre-existing event that worsens, any time after the initiation of the first dosing of the investigational product.

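### No Day 14 safety contact is required for a dosed subject who leaves early, so new adverse events after exit may go undetected

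*Protocol*

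**What the plan says.** Protocol 8.3.1 sets the AE/SAE collection period as running "until completion of study participation (ie, early termination or Follow-up Phone Call", so early termination is an end point in its own right. The same section adds: "Investigators are not obligated to actively seek AEs or SAEs after the conclusion of study participation".

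Protocol 7.2 says of a subject who withdraws or is withdrawn: "The subject will be permanently discontinued both from the study intervention and from the study at that time". Footnote a of the Schedule of Activities (Protocol 1.3) says that "an early termination visit will be performed prior to discharge from the CRU", and describes its content: "The early termination assessments will be the same as those conducted at Discharge (Day 2". It names no later contact.

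Section 7.2 also directs the reader onward: "See SoA for data to be collected at the time of study discontinuation and follow-up". Section 7.1 has a similar pointer. The Schedule contains the Day 14 (+3) call, but it does not say whether that call applies to someone who has left early.

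Several provisions keep known problems in view. Section 7.1 states: "If a subject is discontinuing due to an AE, the AE must be followed until it is resolved, stable", or judged not clinically significant. Sections 6.7 and 8.3.3 continue follow-up for ongoing AEs and other safety concerns. Section 8.3 keeps the investigator responsible for AEs that are serious, related, or a cause of discontinuation. Section 8.3.1 requires a related SAE to be reported if the investigator hears of it later.

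**The concern.** Each subject receives one dose. Leaving afterwards cannot reduce exposure; it only removes observation. The protocol sets follow-up to Day 14 (+3) for those who complete, so it regards that period as relevant to safety. A site that follows 8.3.1, 7.2 and footnote a literally could stop looking for events in an exposed first-in-human volunteer hours after dosing and still be compliant.

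The Safety Analysis Set includes everyone who was given study drug, however little. An early leaver therefore stays in the denominator with less opportunity to contribute events. With 6 active subjects per cohort, one such subject is 1/6 = 17% of a dose group. At stake are complete AE and SAE listings, surveillance of the volunteer and, for the earliest exits, the first-day incidence itself.

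**Working it through.** **The plan's own duration figure.** The synopsis gives total participation as 22 to 45 days. With no Day 0, Day -8 to Day 14 is 8 + 14 = 22 days, and Day -28 to Day 17 is 28 + 17 = 45 days. The figure reproduces, and it assumes that the subject reaches the follow-up call.

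**Two windows that must be kept apart.**
- Collection window for a completer: dosing on Day 1 to the call on Day 14 (+3), which is 14 - 1 = 13 to 17 - 1 = 16 days.
- Planned summary window for the primary endpoints: Protocol 9.4.2 tabulates TEAEs and TESAEs over 1 calendar day postdose, and SAP 7.1 counts new AEs that start within 1 day of the last dose. I take this as 24 hours.

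**Loss for an exit t hours after dosing.**
- Share of the 1-day window lost = max(0, 1 - t/24).
- Days of collection lost = (13 - t/24) to (16 - t/24).

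| Exit after dose | 1-day window lost | Collection days lost |
|---|---|---|
| 4 h | 83% | 12.8 to 15.8 |
| 6 h | 75% | 12.75 to 15.75 |
| 8 h | 67% | 12.7 to 15.7 |
| 12 h | 50% | 12.5 to 15.5 |
| 24 h | 0% | 12 to 15 |
| 72 h | 0% | 10 to 13 |

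At 6 hours the collection loss is 12.75/13 to 15.75/16, about 98%. At 24 hours it is 12/13 = 92% to 15/16 = 94%.

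**What a Day 14 call would add.** For an exit before 24 hours, it could recover first-day events, by recall, for the planned tables. For an exit at or after 24 hours, a new event starting on Days 3 to 14 falls outside those tables even if the call is made. It would reach the SAP 7.1 listings, which cover all subjects with AEs and all SAEs whether or not treatment-emergent. A small exception is an AE with an incomplete start date, which SAP 12.1.4 classes as treatment-emergent when its timing cannot be settled.

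**The definition that does not fit.** Protocol 10.3.1.2 defines a TEAE as an event emerging or worsening "any time after the initiation of the first dosing of the investigational product", with no end. Under that definition the whole 13 to 16 days would count. It conflicts with the 1-day window in 9.4.2 and SAP 7.1.

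**The case against.** The strongest reply has four parts.

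1. **The primary analysis does not run to Day 14.** A reader might infer that an early leaver's primary safety window shrinks from two weeks to hours, and that incidence is biased downward as a result. The documents do not support this. Under 9.4.2 and SAP 7.1, an exit at or after about 24 hours loses none of the summary window, and a 6-hour exit keeps 25% of it. The inference would hold only if the open-ended definition in 10.3.1.2 governed. This objection stands.

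2. **High-risk leavers are not abandoned.** Section 7.2 lets the investigator withdraw a subject on safety grounds, so a reader might infer that those most likely to have later events are cut off. Sections 6.7, 7.1, 8.3 and 8.3.3 point the other way. Discharge may also be delayed (6.7, footnote a), and 8.2.4 asks for clinically significant laboratory abnormalities within 14 days of dosing to be repeated. This also stands. None of these provisions, however, has the site ask about new events in a leaver with no known problem.

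3. **Silence is not prohibition.** Sections 7.1 and 7.2 refer to the Schedule for follow-up, and the Schedule contains the call. It is fair to say that no call is required, but not that none will be made. Still, 8.3.1 does more than stay silent: it ends collection and releases the investigator from seeking later events.

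4. **Few subjects are affected.** Confinement lasts at least 24 hours after dosing, and 7.1 and 7.2 expect withdrawal to be rare. After Day 2 the only scheduled contact left is the call, so many later exits would be withdrawals or losses that no call can reach. This stands and limits the size of the point.

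**Conclusion.** The point holds as a gap in active detection of new AEs and SAEs in a dosed subject who leaves early. Exits within 24 hours forgo about 12 to 16 of the 13 to 16 days of collection that a completer has. The planned primary summary is affected only by exits before about 24 hours, and a 6-hour exit loses 75% of that day. For later exits, the loss is confined to the AE and SAE listings and to surveillance of the volunteer.

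The practical size is small. The documents give no dropout rate but expect early exit to be rare. No hypothesis is tested (9.1), and escalation decisions rest on data through Day 2 (6.6), so a missed Day 14 call does not alter them. The 1-in-6 figure describes one hypothetical subject, not an expected loss.

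The conclusion rests on two assumptions. The first is that the 1-day window is 24 hours from dosing. If the calendar-day wording in 9.4.2 was meant to run to the end of Day 2, the cut-off moves some hours later but not beyond Day 2. The second is that 9.4.2 and SAP 7.1, rather than 10.3.1.2, govern the analysis. This is a worthwhile, inexpensive improvement rather than a flaw that threatens the study.

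**What to change.** - In Protocol 8.3.1, 7.2 and footnote a of the Schedule of Activities, state that any subject who received study drug and leaves early still gets the scheduled Day 14 (+3) safety phone call unless consent to contact is withdrawn. State that AE/SAE collection runs to that call.
- In the AE listing, flag subjects not reached and give their postdose observation time. SAP 6.6 already lists the date and time of dosing, so only the last contact needs adding.
- Separately, reconcile the open-ended TEAE definition in Protocol 10.3.1.2 with the 1-day window in Protocol 9.4.2 and SAP 7.1, so that it is clear which events enter the primary tables.

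The cost is a few sentences, a listing flag and one call per early leaver. Some calls will go unanswered, and events recalled after two weeks will be less precisely dated.

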8.3.2. Method of Detecting AEs and SAEs

The method of recording, evaluating, and assessing causality of AEs and SAEs, and the procedures for completing and transmitting SAE reports are provided in Appendix 3/Section 10.3.

Care will be taken not to introduce bias when detecting AEs and/or SAEs. Open-ended and nonleading verbal questioning of the subject is the preferred method to inquire about AE occurrences.

8.3.3. Follow-up of AEs and SAEs

After the initial AE/SAE report, the investigator is required to proactively follow each subject at subsequent visits/contacts. Subjects with ongoing AEs or other safety concerns will be followed until resolution or until no further queries or follow-up actions are required. All SAEs will be followed until resolution, stabilization, the event is otherwise explained, or the subject is lost to follow-up (as defined in Section 7.3). Further information on follow-up procedures is provided in Appendix 3/Section 10.3.3.

8.3.4. Regulatory Reporting Requirements for SAEs

- Prompt notification by the investigator to the sponsor of an SAE is essential so that legal obligations and ethical responsibilities towards the safety of subjects and the safety of a study intervention under clinical investigation are met.
- The sponsor has a legal responsibility to notify both the local regulatory authority and other regulatory agencies about the safety of a study intervention under clinical investigation. The sponsor will comply with country-specific regulatory requirements relating to safety reporting to the regulatory authority, institutional review boards (IRBs)/independent ethics committees (IECs), and investigators.
- For all studies except those utilizing medical devices, investigator safety reports must be prepared for suspected unexpected serious adverse reactions (SUSARs) according to local regulatory requirements and sponsor policy and forwarded to investigators as necessary.
- An investigator who receives an investigator safety report describing an SAE or other specific safety information (eg, summary or listing of SAEs) from the sponsor will review and then file it along with the IB and will notify the IRB/IEC, if appropriate according to local requirements.

8.3.5. Pregnancy

This study is enrolling males and females of non-childbearing potential.

- Details of all pregnancies in female subjects and female partners of male subjects will be collected after the start of study intervention and either until completion of the Follow-up Phone Call or until the details regarding the pregnancy outcome are reported. The CRU should make a reasonable effort to follow any pregnant patients until delivery or end of the pregnancy.
- If a pregnancy is reported, the investigator should inform the sponsor within 24 hours of learning of the pregnancy and should follow the procedures outlined in Appendix 4/Section [10.4](#).
- Abnormal pregnancy outcomes (eg, spontaneous abortion, fetal death, stillbirth, congenital anomalies, ectopic pregnancy) are considered SAEs.

8.3.6. Cardiovascular and Death Events

Cardiovascular and death events should be reported according to the definitions and reporting procedures for AEs and SAEs outlined in Appendix 3/Section [10.3](#).

8.3.7. Disease-related Events and/or Disease-related Outcomes Not Qualifying as AEs or SAEs

Not applicable to this study in healthy volunteers.

8.3.8. Adverse Events of Special Interest

Not applicable.

8.4. Treatment of Overdose

For this study, any dose of study drug greater than 1 dose of study drug within a 24-hour time period will be considered an overdose.

The sponsor does not recommend specific treatment for an overdose.

In the event of an overdose, the investigator should:

1. Report any case of overdose to the sponsor and use their clinical judgment to treat the case of overdose as needed with the appropriate general supportive measures. Subjects will be monitored for potential development of diarrhea and dehydration and, if present, will be managed accordingly.
2. Document the quantity of the excess dose as well as the duration of the overdose in the CRF.

